7.4. Information to Study Personnel

The Investigator is responsible for giving information about the study to all staff members involved in the study or in any element of subject management, both before starting the study procedures and during the study (e.g., when new staff become involved). The Investigator must ensure that all study staff members are qualified by education, experience, and training to perform their specific responsibilities.

The Sponsor or its designee is responsible for explaining the CIP to all study staff, including the Investigator, and for ensuring their compliance with the protocol throughout the study. Additional information will be made available during the study when new staff become involved in the study, and as otherwise agreed upon with either the Investigator or the monitor.

8. RISK-BENEFIT ANALYSIS

8.1. Risks to the Subjects

The list below described the general types of potential risks to the study subjects.

Adverse Events
Infection
Inflammation
Pain or discomfort
Serous wound drainage
Hematoma
Ecchymosis
Extrusion
Retrieval
Foreign body reaction
Foreign body sensation
Device Fracture
Device Malposition or Migration
Device Palpable
Skin Irritation
Allergic reaction to device
Allergic reaction to medications from procedure or follow up
Allergic reaction to any study related medications
Hematoma*, general (such as cannula insertion, delivery of anesthetics, manipulation of nose during procedure, etc.)
Perceptible cosmetic changes
Respiratory / sinus infection or rhinorrhea
Continued or worsened breathing symptoms
Scarring
Firmness, swelling, redness
Decreased sense of smell

*Includes hematoma from cannula insertion, delivery of anesthetics, manipulation of nose during procedure)

There are other health risks and discomforts associated with the testing that the subjects will undergo before and after their procedure, including but not limited to pain and bruising at the implant pierce point site or areas of anesthetic injections.

For subjects in the Sham Control Group, the use of anesthetic and insertion of the cannula imparts the same risks except for those directly attributable to an implant, without the potential benefit of the treatment.

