3.3. Secondary Endpoints

The following endpoints comprise the secondary endpoints and the time points that each will be assessed:

- Responder Rate at 7 days, 30 days, and 6, 12, 18 and 24 months;
- Frequency of procedure-related adverse events (non-serious and serious), assessed at the index procedure and through the 7-day, 30-day, 3-month, 6-month, 12-month, 18-month, and 24-month follow-up time points;
- Frequency of device-related adverse events (non-serious and serious), assessed at the index procedure and through the 7-day, 30-day, 3-month, 6-month, 12-month, 18-month and 24-month follow-up time points;
- NOSE score, change from baseline, to the 7-day, 30-day, 3-month, 6-month, 12-month, 18-month, and 24-month follow-up time points;
- Visual Analogue Scale (VAS), change from baseline, to the 7-day, 30-day, 3-month, 6-month, 12-month, 18-month, and 24-month follow-up time points;
- Endoscopic lateral wall insufficiency (LWI) score as assessed by independent reviewers, change from baseline to the 3-month and 6-month time points;
- Epworth Sleepiness Scale (ESS) score and Pittsburg Sleepiness Quality Index, change from baseline, to the 7-day, 30-day, 3-month, 6-month, 12-month, 18-month, and 24-month follow-up time points.

All secondary endpoints will be assessed for the Sham Control Arm at two additional visits. The Sham arm will have follow-up visits at 7 days, 30 days, and 3 months after the initial treatment/randomization, and 30 days, 3 months, 6, months, 12 months, 18 months, and 24 months in subjects that cross over.

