6.4. Sample Size

The primary analysis will be based on a 1-sided binomial test of proportions. Assuming a Sham Control response rate of 40% and a Latera Treatment response rate of 70% at month 3, a maximum sample size of 124 evaluable subjects is required for 90% power and preserving a 2.5% (one-sided) type I error rate. This study is designed as a group-sequential trial with 2 interim analyses and a final analysis. The stopping boundaries are derived using the Triangular Method [1], which is a special case of Unified Family (Power) boundaries. A shape parameter of 0.65 will be used, and both boundaries will be non-binding.

Interim analyses will occur when approximately 20 and 60 total subjects have been enrolled. The Latera response rate has been observed at approximately 85% in single-arm trials, and is likely to be slightly lower in a single blind setting. Thus, 70% is likely a conservative estimate. The placebo response rate observed in pain trials is approximately 30%, and may be even higher in a procedural setting, so 40% was selected for the control response rate used in the study design calculations.

Assuming up to a 10% drop out rate and a 10% potential retrieval rate, the sample size is adjusted up to 150 subjects will be enrolled to assure adequate sample size with 3 months follow up will be enrolled.

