9. ASSESSMENTS OF SAFETY

9.1. Defining Adverse Events

An adverse event is an untoward medical occurrence or exacerbation of an existing medical condition subsequent to the experimental therapy. Adverse events are rated in several ways:

- Severity (mild, moderate, severe)
 - *Mild*: No limitation of usual activities, no therapy or only symptomatic therapy required to treat the injury or illness.
 - o Moderate: Some limitation of usual activities or specific therapy is required.
 - Severe: Inability to carry out usual activities, hospitalization, emergency treatment, life threatening events, or death.
- Anticipated (anticipated, unanticipated)
- Device and procedure relationships (unrelated, possibly related, definitely related, or relationship unknown)
 - Unrelated: The clinical event is completely independent of study procedure/study device and/or evidence exists that the event is definitely related to another etiology.
 - Possibly related: The clinical event occurs within a reasonable time sequence to study procedure/study device and there is some evidence to "possibly" suggest a causal relationship. However, the influence of other factors such as underlying disease, concomitant medications, or concurrent treatment may have contributed to the event.
 - Definitely related: The clinical event occurs in a plausible time relationship to study procedure/study device and cannot be explained by any concurrent disease or other devices, drugs or chemicals.
 - *Relationship unknown:* The relationship to the study procedure/study device is not known.

Adverse events will be categorized as either serious or non-serious. A Serious Adverse Event (SAE) is an event that meets at least one of the following:

- Is fatal
- Is life-threatening
- Results in persistent or significant disability/incapacity
- Results in permanent impairment of a body function or permanent damage to a body structure
- Results in hospitalization or prolongs a hospitalization
- Necessitates medical or surgical intervention to preclude permanent impairment of a body function or permanent damage to a body structure

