An adverse device effect (ADE) is any unwanted and unintended response to a medical device. This definition includes any event resulting from insufficiencies or inadequacies in the instructions for use or the deployment of the device and any event that is a result of user error. A serious adverse device effect (SADE) is an adverse device effect that has resulted in any of the consequences characteristic of a serious adverse event or that might have led to any of the consequences if suitable action had not been taken or intervention had not been made or if circumstances had been less opportune. An unanticipated adverse device effect (UADE) is defined as "any serious adverse effect on health or safety or any life-threatening problem or death caused by, or associated with, a device, if that effect, problem, or death was not previously identified in nature, severity, or degree of incidence in the investigational plan or application (including a supplementary application), or any other unanticipated serious problem associated with the device that relates to the rights, safety, or welfare of subjects."

Section 8.1 includes a list of possible adverse events associated with nasal interventions. These events are considered reportable at all time points throughout the trial and require submission to the Sponsor within 1 business day of receipt of information. It is recognized that adverse events may not be reported by the study subject until their follow up visits due to the low risk nature of the potential events.

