9.2. Reporting of Adverse Events

In addition to events considered in the primary efficacy and primary safety analyses, all device- and/or procedure-related adverse events must be captured on the Adverse Event Case Report Form. The report should include, wherever possible, severity, duration, outcome, and the Investigator's written medical judgment as to the relationship of the adverse event to the study device, procedure, or underlying disease (i.e., not related, possibly related, definitely related, or relationship unknown).

All SAEs must be reported to the Sponsor or its Contract Research Organization (CRO) within 1 business day of the Investigator's knowledge of the event. The event is reported in the electronic data capture system. IRB notification of the adverse event may also be required, depending on the conditions of approval or requirements of the respective committee. Any unanticipated adverse device effects must be reported to the Sponsor/CRO within 1 business day from when the Investigator first learns of it.

Non-serious reportable adverse events are to be submitted via the electronic data capture system, also, within 1 business day of learning about the event. Certain reportable events may require adjudication; therefore, supporting documentation must be sent to the Sponsor/CRO.

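### Persisting breathing symptoms are listed as a reportable adverse event, yet the adverse event definition does not clearly cover an unchanged condition, so lack of efficacy can enter the safety data

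*Protocol*

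**What the plan says.** Protocol Section 8.1 gives a table of potential risks under the heading of adverse events. One entry is "Continued or worsened breathing symptoms". The section adds that sham subjects carry the same risks apart from those attributable directly to an implant, so the entry applies to both arms.

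Protocol Section 9.1 refers back to that table: "These events are considered reportable at all time points throughout the trial and require submission to the Sponsor within 1 business day". The sentence has no condition on relatedness. The same section opens with the definition: "An adverse event is an untoward medical occurrence or exacerbation of an existing medical condition subsequent to the experimental therapy".

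Section 9.2 states a narrower duty: "all device- and/or procedure-related adverse events must be captured on the Adverse Event Case Report Form". Section 9.3 has the Medical Monitor assess every event for relatedness and seriousness, and the monitor's classification overrides the site's. Section 3.3 of the protocol and Section 3.2 of the SAP define two safety endpoints, both secondary: the frequency of procedure-related and of device-related adverse events. SAP Section 5.3 compares binary secondary endpoints between arms with a two-sided test.

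Neither document says whether unchanged baseline obstruction is an adverse event or only a lack of efficacy. Neither says whether events classed as possibly related, or of unknown relationship, count as related in the two endpoints.

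**The concern.** Nasal obstruction is the condition under treatment, and inclusion criterion 5 requires a NOSE score of at least 55. Symptoms that continue are therefore the baseline condition persisting, which the primary endpoint already measures through NOSE. A site that follows the list in 8.1 would report such a subject within one business day. A site that follows the definition in 9.1 would report only worsening. Both could claim to be following the protocol.

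The plan expects failure to respond to be more common on sham. If some persisting symptoms are recorded as adverse events, part of the expected efficacy difference can carry over into a safety table. The Data Monitoring Committee reviews safety data in aggregate (Section 9.4), and nothing limits that review to related events. Differences in practice between sites would add noise. What is at stake is how cleanly the adverse event frequencies can be read; the primary analysis is not affected.

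**Working it through.** **The plan's own figure.** The documents state no adverse event rate by arm for this trial, so there is no safety figure to reproduce. The design figures used here come from Section 6.4: "Assuming a Sham Control response rate of 40% and a Latera Treatment response rate of 70% at month 3", with 124 evaluable subjects. Simulating the three looks at 22, 60 and 124 with the tabulated boundaries gives 90.2% power when futility stops are followed and a one-sided type I error of 0.0251 when they are ignored. That agrees with the stated 90% and 2.5%. With 1:1 allocation there are 124 / 2 = 62 subjects per arm.

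**Inputs**
- Non-response at 3 months: sham 1 − 0.40 = 60%; Latera 1 − 0.70 = 30%.
- f: the share of non-responders whose persisting symptoms are recorded and judged procedure-related. Not in the documents, so shown as a range and taken as equal in both arms.
- b: the background rate of other related events, assumed independent of response. Also assumed.

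**Procedure-related events, before overlap.** Added sham-minus-Latera difference = f × (60 − 30) = f × 30 points.

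| f | Added difference (points) |
|---|---|
| 0% | 0 |
| 5% | 1.5 |
| 10% | 3 |
| 25% | 7.5 |
| 50% | 15 |
| 100% | 30 |

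**With overlap.** Rate per arm = 1 − (1 − b)(1 − f × non-response). With b = 10% in both arms:
- f = 10%: Latera 1 − 0.90 × 0.97 = 12.7%; sham 1 − 0.90 × 0.94 = 15.4%.
- f = 50%: Latera 1 − 0.90 × 0.85 = 23.5%; sham 1 − 0.90 × 0.70 = 37.0%.
- f = 100%: Latera 1 − 0.90 × 0.70 = 37.0%; sham 1 − 0.90 × 0.40 = 64.0%.

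With 62 per arm, the chance of a significant two-sided 5% difference (normal approximation) is about 6%, 37% and 86% respectively.

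**When could the order of the arms change?** Suppose the true background were 10% on Latera and 5% on sham. The rates are equal when 0.90(1 − 0.3f) = 0.95(1 − 0.6f), that is 0.30f = 0.05, so f is about 17%. With 13% on Latera (the per-subject device-related rate in the first 30-subject study, Section 1.2) and 5% assumed on sham, 0.87(1 − 0.3f) = 0.95(1 − 0.6f) gives 0.309f = 0.08, so f is about 26%.

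**If responders are reported too.** A responder needs only a 20% fall in NOSE. A fall from 75 to 60 is 15/75 = 20%, a response, yet 60 still meets the entry threshold. If a share g of responders is also reported and judged related, the added rates are 0.60f + 0.40g on sham and 0.30f + 0.70g on Latera. The difference is 0.30 × (f − g). The f × 30 figure therefore assumes g = 0, and the distortion shrinks as g approaches f.

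**Device-related events.** Sham subjects receive no implant, so persisting symptoms judged implant-related can add only to Latera. From an assumed 5% base, Latera becomes 1 − 0.95 × 0.97 = 7.85% at f = 10% and 1 − 0.95 × 0.70 = 33.5% at f = 100%, against 0% on sham.

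**The case against.** The strongest reply is that reportable does not mean counted. Both safety endpoints require relatedness, the Medical Monitor decides it centrally, and obstruction documented at baseline could readily be classed as unrelated. This largely stands, and it is why no size can be fixed. It does not close the gap: the monitor has no stated rule for lack of efficacy and is not stated to be blinded to arm, the investigator knows the assignment, and the treatment of possibly related and unknown events in the endpoints is undefined.

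A second reply is that Section 8.1 is a list of general risks, to be read subject to the definition in 9.1. That is a reasonable reading, but the text does not state it, and the reportability sentence points the other way.

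Third, the first study is mildly reassuring. At 3 months 25 of 29 subjects had responded, so 4 had not, yet its five device-related events were three extrusions, one hematoma and one inflammation. None was persisting symptoms. That study's reporting rules are not shown, so this is only indicative.

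A reader might go further and infer that every treatment failure counts as a safety event, so that the comparison is tilted by the whole efficacy difference: 62 × 0.60, about 37 sham subjects, against 62 × 0.30, about 19 on Latera. The documents do not support this. It needs every non-responder and no responder to be both reported and judged related. Nor do they support the inference that real harm would be hidden: events are MedDRA-coded, so an extrusion or infection stays identifiable, and the committee also sees interim efficacy.

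A reader might also infer from the wording about experimental therapy that sham subjects fall outside the definition. In practice adverse events are collected after consent, at the procedure in both arms and at each follow-up visit (Sections 5.1 and 5.2, Table 2).

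**Conclusion.** The conflict between Sections 8.1 and 9.1 is real, and nothing in the protocol or SAP resolves it. Sites may report persisting symptoms differently, and lack of efficacy may enter the adverse event data. The effect on the two safety endpoints is conditional on the Medical Monitor's relatedness judgment. For procedure-related events it is about f × 30 points against sham before overlap, assuming the 40% and 70% response rates, equal f in both arms and no responders reported. It is 3 points at f = 10% and 15 at f = 50%; 30 points is the extreme case, not the expectation. For device-related events any distortion would run against Latera. A change in the order of the arms is possible only under assumed background rates and a fairly large f (about 17% to 26% in the examples). The concurrent sham comparison ends at 3 months, when subjects are unblinded and sham subjects may cross over, so the point concerns safety data up to then. This is worth correcting before the adverse event data are tabulated, but it does not threaten the primary conclusion.

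**What to change.** In the protocol, reconcile 8.1 with 9.1. State that persistence of baseline obstruction remains a disclosed risk but is an efficacy outcome captured through NOSE, and that only worsening from baseline is reportable as an adverse event. Carry the same rule into the CRF completion guidelines and the Medical Monitor's instructions.

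In the SAP, tabulate worsened breathing on its own line, and keep any report of merely unchanged symptoms out of the procedure- and device-related frequencies.

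Optionally, align the definition's reference to the experimental therapy with the collection already done in both arms.

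The cost is a few sentences in an amendment and somewhat less site reporting. No efficacy information is lost, because Protocol Table 2 collects NOSE at every follow-up visit.

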8.2. Risk Mitigation

The subject risks for participation in the Lateral RCT Study are mitigated through device design, protocol development, and study conduct methods.

The Latera Implant is designed and indicated for use to support of the lateral nasal cartilages. The device will be used as directed in the FDA Cleared Indications for Use. The device has been commercially available in the US for over a year and used in three (3) clinical studies with consistent high efficacy and low complication rates, as described previously.

The Latera RCT is a Group Sequential Study. This is an adaptive study design that allows for interim data review for potentially halting enrollment for early demonstration of success or for futility (inability to reach the primary objectives). Additionally, although the treatment assignment is blinded to the study subjects, an independent Data Monitoring Committee will be reviewing the data at pre-determined interim analyses to determine if the study is operationally sound or meets pre-determined success criteria, limiting randomization to no more subjects than are required to meet the primary objectives.

Risk mitigation through study operations include the selection of experienced investigators with the appropriate research infrastructure, providing training and data monitoring to limit protocol deviations and operational execution. The study includes IRB review and approval of the study protocol, informed consents for appropriate risk disclosure, and the patient brochure and study poster to assure the study meets clinical research standards and regulatory requirements.

The measures listed above will be implemented in this study to mitigate potential risks to the study subjects.

8.3. Benefit to Subjects

The Latera implant has been successfully deployed in over 7,000 patients in the past year, including over 300 in a research setting. This has enabled a high proportion to have a reduction in nasal obstruction symptoms with a low complication rate. This benefit may be afforded to the subjects that participate in this study. Subjects may also benefit from the additional monitoring and follow-up evaluations mandated by this study protocol. The Sham Control subjects have the opportunity to cross-over, if these symptoms persist and they remain eligible for the Latera Implant in this study. Those subjects will have the same potential benefit at that point as those randomized to the Latera Implant arm.

8.4. Study Justification

Nasal valve collapse (NVC) due to lateral wall weakness is significant contributor to NAO. The Latera Implant offers a minimally invasive treatment to support the lateral cartilages. The Latera RCT provides the opportunity to rigorously assess the impact of the implant itself in alleviating the symptoms of NVC due to lateral nasal wall weakness. Patients with other primary contributors to NAO will not be included such as septal conditions or turbinate hypertrophy since these potentially mask the full impact of the Latera Implant. Three (3) prospective, single-arm studies have continued to show the high rate of

reduction in nasal obstruction and low complications rates as well as support the study design for superiority.

9. ASSESSMENTS OF SAFETY

9.1. Defining Adverse Events

An adverse event is an untoward medical occurrence or exacerbation of an existing medical condition subsequent to the experimental therapy. Adverse events are rated in several ways:

- Severity (mild, moderate, severe)
 - *Mild*: No limitation of usual activities, no therapy or only symptomatic therapy required to treat the injury or illness.
 - o Moderate: Some limitation of usual activities or specific therapy is required.
 - Severe: Inability to carry out usual activities, hospitalization, emergency treatment, life threatening events, or death.
- Anticipated (anticipated, unanticipated)
- Device and procedure relationships (unrelated, possibly related, definitely related, or relationship unknown)
 - Unrelated: The clinical event is completely independent of study procedure/study device and/or evidence exists that the event is definitely related to another etiology.
 - Possibly related: The clinical event occurs within a reasonable time sequence to study procedure/study device and there is some evidence to "possibly" suggest a causal relationship. However, the influence of other factors such as underlying disease, concomitant medications, or concurrent treatment may have contributed to the event.
 - Definitely related: The clinical event occurs in a plausible time relationship to study procedure/study device and cannot be explained by any concurrent disease or other devices, drugs or chemicals.
 - *Relationship unknown:* The relationship to the study procedure/study device is not known.

Adverse events will be categorized as either serious or non-serious. A Serious Adverse Event (SAE) is an event that meets at least one of the following:

- Is fatal
- Is life-threatening
- Results in persistent or significant disability/incapacity
- Results in permanent impairment of a body function or permanent damage to a body structure
- Results in hospitalization or prolongs a hospitalization
- Necessitates medical or surgical intervention to preclude permanent impairment of a body function or permanent damage to a body structure

An adverse device effect (ADE) is any unwanted and unintended response to a medical device. This definition includes any event resulting from insufficiencies or inadequacies in the instructions for use or the deployment of the device and any event that is a result of user error. A serious adverse device effect (SADE) is an adverse device effect that has resulted in any of the consequences characteristic of a serious adverse event or that might have led to any of the consequences if suitable action had not been taken or intervention had not been made or if circumstances had been less opportune. An unanticipated adverse device effect (UADE) is defined as "any serious adverse effect on health or safety or any life-threatening problem or death caused by, or associated with, a device, if that effect, problem, or death was not previously identified in nature, severity, or degree of incidence in the investigational plan or application (including a supplementary application), or any other unanticipated serious problem associated with the device that relates to the rights, safety, or welfare of subjects."

Section 8.1 includes a list of possible adverse events associated with nasal interventions. These events are considered reportable at all time points throughout the trial and require submission to the Sponsor within 1 business day of receipt of information. It is recognized that adverse events may not be reported by the study subject until their follow up visits due to the low risk nature of the potential events.

